#### 3.2.2.2 Exclusion Criteria

Those who do not meet any of the above conditions are excluded.

Reason: The included non-small cell lung adenocarcinoma samples and normal samples should have statistical significance, and the conclusions obtained should be scientific and valid. The selection of subjects for this study, while excluding research-related influencing factors, has no adverse effect on the health of the subjects.

#### 3.2.2.3 Rejection Criteria

- (1) Samples considered by the researcher to be unsuitable for continuing clinical trials, such as samples that have not been prepared in accordance with the required steps.
- (2) The amount of DNA and RNA extracted from the sample is insufficient, and the clinic can no longer provide more tissues for the extraction of DNA and RNA samples.
- (3) Samples whose results failed in repeated detections by the contrast method.
- (4) Sample patients with incomplete clinical basic information (visiting number/medical record number/specimen number, age, gender, pathological diagnosis results).
- (5) Samples that cannot be completed in a single test due to instrument or human factors (samples are contaminated during operation).

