## 3 Trial Design

#### 3.1 Overall Design of the Trial

This trial follows the principle of synchronous blinding. The enrolled cases are coded, and the enrolled samples are detected with the Genetron Lung Cancer Panel and comparison methods. The

detection results are compared, and the samples that are inconsistent with the detection results of similar products on the market are reviewed by the Sanger sequencing method, when the site detection results compared with Sanger sequencing method are inconsistent, Sanger's detection results are recognized. The results were determined independently according to the cutoff values or interpretation requirements provided by each method, and relevant statistics were used to evaluate clinical application performance of

Genetron Lung Cancer Panel.

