#### 3.2 Clinical Trial Sample Screening

#### 3.2.1 Sample Type and Size

The samples in this study are confirmed tissue biopsy samples, which are retrospective samples.

The total number of samples in this clinical trials is 1052. It is planned to be carried out in at least 4 clinical trial institutions, and 3 of them will enroll no less than 255 samples. In case of objective reasons, when the sample size is insufficient, the centers can make appropriate adjustments or increase clinical trial institutions under the premise of ensuring the total amount. It is planned that the ratio of positive samples shall not be less than 30%, and the rare mutation types shall be counted according to the clinical occurrence, which should be statistically significant. Gene locus below the above standards can no longer be included in clinical data statistics.

The analysis of the selected number of case samples is statistically significant, and the conclusions obtained are reasonable and effective, which can make a scientific evaluation of the Genetron Lung Cancer Panel and save social costs to the greatest extent. If all types of specimens are not received as planned due to other reasons, the final type and quantity of specimens shall be subject to the actual collected specimens after negotiation and agreement between the two parties.

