### 4 Statistical Analysis

#### 4.1 The coincidence rate of the panel and the comparison method

For each gene locus, a four-grid table was used to calculate the positive coincidence rate, negative coincidence rate, positive predictive value, negative predictive value, total coincidence rate and 95% confidence interval of the assessment reagent and the comparison method. Using statistical software, Kappa test is used to determine whether the two detection methods are statistically significant.

Table 2. Results statistics

Genetron Lung Cancer	Comparison method		Total
Panel	Positive	Negative	
Positive	A	В	A+B
Negative	C	D	C+D
Total	A+C	B+D	A+B+C+D

A sample with a mutation genotype is judged as positive, and a sample with no mutation genotype is judged as negative

The calculation formula is:

Positive coincidence rate=A/(A+C)×100%

Negative coincidence rate =  $D/(B+D) \times 100\%$ 

Positive predictive value (PPV)=A/(A+B)×100%

Negative predictive value (NPV)=D/(C+D)×100%

Total coincidence rate=(A+D)/(A+B+C+D)×100%

95% confidence interval calculation formula:  $p\pm1.96\times[p(1-p)/n]^{1/2}$  (where p is the positive coincidence rate, negative coincidence rate, positive predictive value, negative predictive value, total coincidence rate, n is the sample size, if p>0.9, use Wilson score method for correction).

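### Criterion (3) rejects the whole sample when one gene's comparator fails, and samples with no valid panel result have no place in the per-locus tables

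*Combined protocol and SAP*

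**What the plan says.** Section 3.2.2.3 lists five rejection criteria, all worded in terms of samples. Three matter here:

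- Criterion (1): "Samples considered by the researcher to be unsuitable for continuing clinical trials". The example given is a preparation fault.
- Criterion (3): "Samples whose results failed in repeated detections by the contrast method". No gene or locus is named.
- Criterion (5): "Samples that cannot be completed in a single test due to instrument or human factors". The example given is contamination during handling. The criterion does not say whether the test is the panel, a comparator or either.

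The analysis uses a different unit. Section 4.1 states: "For each gene locus, a four-grid table was used to calculate the positive coincidence rate". Table 1 in section 3.3.2 assigns comparators by gene: EGFR, ALK, ROS1, KRAS, PIK3CA and BRAF each have a kit or probe. The instrument list below it gives Sanger sequencing for MET and HER2. Table 2 in section 4.1 has two result categories, positive and negative, for each method.

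On sample size, section 3.2.1 says: "The total number of samples in this clinical trials is 1052". No allowance for rejected samples is stated. No section asks for a panel failure rate, a per-gene analysis set or a log of rejections.

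**The concern.** There are two separate problems.

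**Unit mismatch.** A rule at sample level is applied to an analysis at locus level. If ALK FISH fails twice, the literal text removes that sample's EGFR, KRAS and other pairs too, although both methods gave a result for them. Inclusion criterion (3) in section 3.2.2.1 takes the FISH slices separately from the DNA/RNA material, so a FISH failure need not say anything about the PCR or sequencing results. The loss could matter most for rare variants: section 3.2.1 drops a locus from the statistics if it falls below that section's standards, and positives lost to an unrelated assay could contribute to that.

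**No place for a panel no-result.** Section 3.2.2.3 has an explicit rule for comparator failure but none for an invalid panel result. Such a sample may leave under criterion (5), or simply not appear, because Table 2 has no cell for it. Section 2 sets out to establish the panel's accuracy as a companion diagnostic for EGFR, ALK and ROS1, so how often the panel gives no answer is itself a performance result. If no-results come mainly from poor tissue, where the panel is also more likely to err, the remaining samples will look better than the full set.

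**Working it through.** **Inputs from the documents.** N = 1052 (section 3.2.1). There are six comparators with a named kit or probe, and eight with Sanger for MET and HER2 (section 3.3.2). At least 30% of samples are planned to be positive (section 3.2.1), so 0.30 × 1052 = 315.6, or 316.

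**Assumed.** The documents give no assay failure rate. I take f = 1% to 3% per comparator, equal across assays, and assume every sample receives every comparator. Section 3.1 suggests the latter but does not state it. The figure of 1052 cannot be reproduced, because no target rate, precision, power or rejection allowance is given. It serves only as the base.

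**Step 1: loss under the literal criterion (3).** With k comparators the share of samples lost lies between two cases:

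- Failures fully overlapping (the same samples fail every assay): loss = f.
- Failures independent: loss = 1 − (1 − f)^k.

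| | f = 1% | f = 3% |
|---|---|---|
| Per-gene rule, loss per table | 1% (about 11) | 3% (about 32) |
| Whole-sample rule, full overlap | 1% (about 11) | 3% (about 32) |
| Whole-sample rule, independent, k = 6 | 5.9% (62) | 16.7% (176) |
| Whole-sample rule, independent, k = 8 | 7.7% (81) | 21.6% (228) |

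For k = 8: 1 − 0.99^8 = 0.0773, and 0.0773 × 1052 = 81.3. Likewise 1 − 0.97^8 = 0.2163, and 0.2163 × 1052 = 227.5. The k = 6 row applies if Sanger for MET and HER2 is not counted as a comparison method under criterion (3).

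The avoidable loss is the gap between the whole-sample rows and the first row. It is zero under full overlap and largest under independence.

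**Step 2: panel no-results and the positive coincidence rate.** Suppose 97 of 100 comparator-positive samples with a valid panel result agree, and 5 more comparator-positive samples have no valid panel result.

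- Dropped: 97/100 = 97.0%.
- Counted as not detected: 97/105 = 92.4%.

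The same comparison on 316 positives, with 9 misses among those with a valid panel result:

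| Panel no-results | Dropped | Counted as not detected |
|---|---|---|
| 1% (3) | 304/313 = 97.1% | 304/316 = 96.2% |
| 5% (16) | 291/300 = 97.0% (Wilson 95% CI 94.4 to 98.4) | 291/316 = 92.1% (88.6 to 94.6) |
| 10% (32) | 275/284 = 96.8% | 275/316 = 87.0% |

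The 316 is the planned minimum of positive samples overall, not the count at any one locus, so it only shows the scale. The first column is agreement given a valid call. The second is agreement when a no-result counts as a failure to detect. The plan as written would report only the first and would not show how far apart they are.

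**The case against.** **Criterion (3) can be read per gene.** Comparators are assigned by gene, the tables are by locus, and section 3.2.1 itself drops a locus rather than a sample. That reading is available, but the text does not settle it, and sites could apply it differently. The point stands as a needed clarification.

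**The independent-failure figures are an upper case.** If failures concentrate in poor tissue, as the bias argument supposes, they overlap and the loss falls towards 1% to 3%. This is right, and 7.7% to 21.6% should not be read as an expected loss.

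**Rejected samples can be replaced.** Section 3.2.1 lets centres adjust, or institutions be added, to keep the total. That may restore numbers, though the same section later defers to the specimens actually collected. It does not undo selection.

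**Criterion (5) concerns instrument and human faults, not poor tissue.** This is fair: an instrument breakdown is not a missed mutation. It leaves sample-related panel failure with no rule at all, and it is why reasons should be reported separately.

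**The only stated threshold is kappa above 0.75 (section 4.2).** A shift in the positive coincidence rate alone breaches no stated criterion. The rates and their intervals are nevertheless reported as the panel's performance.

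**A reader might infer that discordant samples can be rejected to improve agreement.** The documents do not support that. No criterion names discordance, and section 3.1 gives such samples a route: "the samples that are inconsistent with the detection results of similar products on the market are reviewed by the Sanger sequencing method". Criterion (1)'s example is a preparation fault, and section 5 requires both tests to be run blind. What remains is a gap in documentation: criterion (1) is discretionary and has no time limit, and the blind file in section 3.2.4 conceals patient identity rather than discordance once coded results have been compared.

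**Conclusion.** The concern holds in two parts. On its literal wording, criterion (3) discards valid pairs for other genes. Separately, samples with no valid panel result can leave the tables uncounted.

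The size cannot be fixed from the documents. At an assumed 1% to 3% failure per comparator, with all eight run on every sample, the literal rule loses between 1% to 3% and 7.7% to 21.6% of samples, depending on how far failures overlap, against 1% to 3% per table under a per-gene rule. In the illustration, five no-results beside 100 valid positives separate 97.0% from 92.4%. Upward bias is plausible but not shown.

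It would go too far to say that the rejection criteria in general act on test results. Criterion (2) concerns nucleic acid yield and criterion (4) clinical records. Criteria (3) and (5) act at or after testing, and criterion (1) may.

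**What to change.** Amend sections 3.2.2.3 and 4.1 as follows.

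- (a) **Criterion (3).** A comparator that fails after repeat removes the sample from that gene's table only. Its valid pairs for other genes stay in.
- (b) **Panel no-results.** Keep in the study any sample with a valid comparator result but no valid panel result. Report the panel no-result rate per gene, separating instrument or human faults from sample or assay failure. Add a sensitivity analysis that counts no-results as non-agreement in the denominators of the positive, negative and total coincidence rates only. Leave PPV and NPV on valid panel calls: adding no-results to cells B or C would lower PPV or NPV for calls the panel never made.
- (c) **Rejections.** List every rejection under criteria (1) and (5) with its reason and whether it came before or after the results were compared.

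The cost is protocol and SAP wording, a rejection listing and a short additional table per gene. No new samples or assays are needed. The downside is denominators that differ by gene and a slightly lower agreement figure in the sensitivity analysis.

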#### 3.2.3 Sample Collection, Storage, and Transportation Methods

## Sample collection

Samples are collected according to the pathology operation standard, and the paraffin-embedded pathological section samples should be determined to contain more than 50% of tumor cells.

#### Sample storage and transportation

The formalin-fixed paraffin-embedded tissue within the validity period of the sample is transported at room temperature. The extracted nucleic acid is recommended to be detected immediately, otherwise the DNA should be stored below -18°C, the storage time should not exceed 7 months, and the number of freeze-thaw cycles  $\leq$  5 times; RNA should be stored below -70°C, the storage time should not exceed 3 months, and the number of freeze-thaw cycles  $\leq$  5 times.

#### 3.2.4 Sample Code

In principle, one subject only provides one sample, and each subject should have a unique clinical trial number (secondary code). After the samples are entered into the group and before the experiment operation, the blind-editing staff will mark the secondary code outside the sample tube, and carefully record the primary code (patient visit number/medical record number/specimen number) and the correspondence table of the secondary code as the blind bottom save. The blind-editing file is kept independently by the blind-editing staff until the blind is solved. Under no circumstances should the blindness be solved during the tail.

During the experiment operation, only the secondary code of the sample is reflected.

#### 3.3 Product Information for the Clinical Trial

#### 3.3.1 Test Reagent

Reagent name: Genetron Lung Cancer Panel

Manufacturer: Genetron Health (Beijing) Co., Ltd.

Applicable instruments: gene sequencer DA8600, gene sequencer Genetron S5

#### 3.3.2 Comparison Method

The specific sites and corresponding kits are shown in the following table

Table 1. Selection of comparison methods for each gene

Gene	Comparison method		
EGFR	cobas EGFR Mutation Test V2		
ALK	Vysis ALK Break Apart FISH Probe Kit		
ROS1	Vysis 6q22 ROS1 Break Apart FISH Probe		
ROS1*	ROS1 gene fusion detection kit (fluorescence PCR method)		
KRAS	KRAS gene mutation detection kit (fluorescence PCR method)		

PIK3CA	PIK3CA gene mutation detection kit (fluorescence PCR method)
BRAF	BRAF gene mutation detection kit (fluorescence PCR method)
MET	/
HER2	/

\* On the basis of choosing the Vysis 6q22 ROS1 Break Apart FISH Probe kit as a comparison method for the ROS1 gene, add no less than 200 samples for ROS1 gene fusion detection kit (fluorescent PCR method) to perform the comparative study of companion diagnostic reagents.

#### Applicable instrument for comparison method

EGFR, KRAS, BRAF, ROS1 (for fluorescent PCR method): including but not limited to cobas® 4800 System, Stratagene Mx3000P, ABI7500, Bio-rad CFX96;

PIK3CA (for fluorescent PCR method): Stratagene Mx3000P

ALK, ROS1 (FISH method applicable): Break Apart FISH Probe platform;

MET, HER2 (Sanger method applicable): Life 3130/3130xl, 3730xl, 3500Dx, 3500xl Dx.

#### 3.3.3 Review method

Sanger sequencing is used as the review method. Sequencing fragments cover the target nucleic acid segments, sites and corresponding types amplified by the assessment reagent. After the sequencing reaction is over, submit a representative sample sequencing map and result analysis data.

During the trial, different verification methods can be appropriately added according to the specific conditions.

- (1) Product name for clinical trials: Sequencing Kit (Life: BigDye Sequencing Reaction Kit)
- (2) Test equipment: Life 3130/3130xl, 3730xl, 3500Dx, 3500xl Dx

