## 2 Research Purpose

The main purpose of this study is: by evaluating the Genetron Lung Cancer Panel to compare the results of simultaneous detection with similar products on the market and the Sanger sequencing method, and to calculate the coincidence rate and consistency of the assessment reagents and the comparison method. The safety and effectiveness of the product are confirmed and evaluated. Meanwhile, the accuracy of the Genetron Lung Cancer Panel for the following drug companion diagnostic tests: EGFR gene 19 exon deletion and L858R point mutation in gefitinib tablets, erlotinib hydrochloride and icotinib hydrochloride tablets, T790M point mutation in methanesulfonate acid osimertinib tablets, ALK gene fusion and ROS1 gene fusion in crizotinib capsules.

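### For ALK and ROS1, the Sanger review is specified by the panel's own targets, so it is not an independent arbiter of panel misses against FISH

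*Combined protocol and SAP*

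**What the plan says.** Section 3.1 sets the review path. Of the tested samples, "the samples that are inconsistent with the detection results of similar products on the market are reviewed by the Sanger sequencing method", and "when the site detection results compared with Sanger sequencing method are inconsistent, Sanger's detection results are recognized". The rule is general and makes no separate provision for gene fusions.

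Section 3.3.3 defines what the review sequences: "Sequencing fragments cover the target nucleic acid segments, sites and corresponding types amplified by the assessment reagent". It then adds an option: "During the trial, different verification methods can be appropriately added according to the specific conditions".

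Table 1 in section 3.3.2 names the comparators for the two fusion genes: "Vysis ALK Break Apart FISH Probe Kit" for ALK and "Vysis 6q22 ROS1 Break Apart FISH Probe" for ROS1. A fluorescence PCR kit is added for ROS1 in at least 200 samples.

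Section 2 makes these genes part of the companion-diagnostic purpose: "ALK gene fusion and ROS1 gene fusion in crizotinib capsules".

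Section 4.1 defines the positive coincidence rate as A/(A+C) and labels the reference column of Table 2 as the comparison method. Section 4.2 describes the kappa reference as the gold standard in one sentence and as the comparison method in others. Neither section says whether the reference is the result before or after Sanger review.

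**The concern.** An arbiter of discordant results should be able to find against either test. Here its required coverage is taken from one of the two tests being compared. A break-apart probe, as its name indicates, reports that the gene is split and does not look for a listed partner or junction. A review built on the panel's own segments and types need not contain a fragment for a fusion that the panel was not designed to amplify. For such a sample the review can agree with the panel's negative but has no means of contradicting it.

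At stake is the error most relevant to the crizotinib claim, a fusion that the panel misses. Missed fusions sit in cell C, the only cell that pulls A/(A+C) below 100%. A review that relabels some of them as FISH errors moves the rate in the panel's favour only.

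**Working it through.** The plan gives no figure on this point to reproduce, so the check traces the rules and then illustrates their effect.

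**Tracing one sample.** Take a FISH-positive, panel-negative ALK sample whose junction lies outside the panel's design.

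1. It is discordant with the comparator, so section 3.1 sends it to Sanger.
2. Fragments that meet section 3.3.3 cover what the panel amplifies. Nothing requires a fragment that spans this junction, so there may be no product.
3. The plan does not say how a no-product review is recorded. Rejection criterion (3) in section 3.2.2.3 concerns repeated failure of the contrast method, not of the review. Section 4.1 calls a sample without a mutation genotype negative.
4. If no product is read as negative, section 3.1 recognizes it over FISH.
5. If the recognized result then fills Table 2, the sample moves from C to D.

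Steps 1 and 2 follow from the text. Step 3 is silence, and steps 4 and 5 are conditional on how that silence is filled.

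**Inputs.** From the documents: N = 1052 (section 3.2.1); positive coincidence rate A/(A+C), with Wilson limits if p > 0.9 and p ± 1.96 × √[p(1−p)/n] otherwise (section 4.1); kappa criterion 0.75 (section 4.2). Assumed: 40 FISH positives, 4 panel misses, no panel-only positives, everything else concordant.

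**Before review.** A = 36, B = 0, C = 4, D = 1012.
- Positive coincidence rate = 36/40 = 90.0%. The plan's formula at p = 0.9 gives 0.900 ± 1.96 × √(0.9 × 0.1/40) = 0.900 ± 0.093, or 80.7 to 99.3%. Wilson limits would be 76.9 to 96.0%.
- Kappa: Pa = 1048/1052 = 0.9962; Pc = (36 × 40 + 1012 × 1016)/1052² = 0.9304; kappa = (0.9962 − 0.9304)/(1 − 0.9304) = 0.945. (Section 4.2 prints Pc over N; N² is used here.)

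**After review, if all 4 move to D.** A = 36, C = 0, D = 1016. Positive coincidence rate = 36/36 = 100%, with Wilson lower limit 36/(36 + 1.96²) = 90.4%. Kappa = 1.00.

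**If only m of the 4 misses lie outside the design.** Assume Sanger confirms the others as fusions, so that they stay in C. The rate is 36/(40 − m):

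| m | Rate |
|---|---|
| 0 | 90.0% |
| 1 | 36/39 = 92.3% |
| 2 | 36/38 = 94.7% |
| 3 | 36/37 = 97.3% |
| 4 | 100% |

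**Range over assumed prevalence.** FISH positives at 2%, 5% and 10% of 1052, with all misses outside the design:

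| FISH positives | 10% missed | 20% missed | 40% missed |
|---|---|---|---|
| 21 | 19/21 = 90.5% | 17/21 = 81.0% | 13/21 = 61.9% |
| 53 | 48/53 = 90.6% | 42/53 = 79.2% | 32/53 = 60.4% |
| 105 | 95/105 = 90.5% | 84/105 = 80.0% | 63/105 = 60.0% |

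Every entry becomes 100% if Sanger replaces FISH. Kappa before review falls below 0.75 only at the extreme: at 40% missed it is 0.761, 0.743 and 0.730 for 21, 53 and 105 positives. After replacement it is 1.00.

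**The case against.** Several stronger readings are tempting, and the documents do not support them.

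- **That the review covers only the panel's targets.** Section 3.3.3 says what the fragments cover and does not forbid wider ones. What stands is that nothing wider is required.
- **That an out-of-design fusion is ruled negative.** No section equates a no-product reaction with a negative. Section 3.1 refers interpretation to each method's own requirements, so a failed amplification might count as no result. The plan is silent, and silence leaves the unfavourable reading open.
- **That the reported rates are inflated.** This needs the reviewed result to replace FISH in Table 2, whose column is labelled as the comparison method. If unreviewed FISH is used, the inflation is zero. What then remains is that the discordance review may attribute a true panel miss to FISH.
- **That reviewed agreement is always 100%.** This holds only by assuming that every miss is outside the design. Misses within the design that Sanger confirms stay in cell C.
- **That the same happens for point mutations and indels in other genes.** The documents identify no comparator-reported variant that lies outside the panel's segments.

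Two mitigations deserve credit. Extra verification methods are allowed, but with no trigger, named method or precedence over section 3.1. The ROS1 fluorescence PCR comparison adds a second comparator, but not for ALK, and for ROS1 the plan commits to only 200 or more samples.

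FISH can also be falsely positive. That is a reason to list the Sanger result beside the sample, not to let a review without independent coverage decide the cell.

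**Conclusion.** The plan is wrong as written, at should-fix level. For ALK and ROS1 it gives precedence over FISH to a review whose required coverage is set by the panel, without an exception for fusions and without a rule for reviews that yield no product. Following those rules can turn a true panel miss into an apparent FISH error, and for a fusion outside the design the effect runs only in the panel's favour.

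Upward bias in the positive coincidence rate rests on four conditions that the documents do not establish: fragments no wider than the panel's targets, no product read as negative, replacement of FISH in Table 2, and some fusions outside the panel's design. The shift from 90.0% to 100% is therefore an illustration for 40 assumed positives with 4 out-of-design misses, not an estimate. With no partner list, breakpoints or fusion prevalence in the documents, the true size could be close to zero.

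**What to change.** Amend sections 3.1, 3.3.3, 4.1 and 4.2 before unblinding, to state that:

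- the ALK and ROS1 four-grid tables and kappa use the unreviewed FISH result in both directions, for cells B and C alike;
- Sanger results for discordant ALK and ROS1 samples are listed separately and move no sample between cells;
- a Sanger review with no product, or a negative from a fragment that does not cover the alteration the comparator reported, is recorded as uninformative and does not overturn the comparator.

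The symmetry matters. Suppose Sanger could confirm panel-only positives but never overturn FISH positives. With A = 36, B = 4, C = 4, D = 1008, moving B to A would raise positive agreement from 36/40 = 90.0% to 40/44 = 90.9%, and negative agreement from 1008/1012 = 99.6% to 1008/1008 = 100%. That rule would again favour the panel.

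The cost is protocol wording, with no extra tests or tissue. The downside is that reported ALK and ROS1 agreement may be slightly lower, because FISH errors in either direction count against the panel. The separate Sanger listing keeps that evidence visible.
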